## **Intervention**

The guided self-help intervention will consist of six online sessions of self-help information for participants to work through, plus activities to carry out in-between sessions. The intervention will consist of psycho-education material, self-monitoring, and compassion-inducing exercises from CFT (Gilbert, 2010). The self-help exercises in the intervention will be evidence-based as being effective for depression: the compassion-focused imagery exercises will be those used by McEwan and Gilbert (2016) and the letter-writing exercise will be based on the one used by Shapira and Mongrain (2010). Other exercises, such as thought monitoring and relapse prevention planning, are commonly used in CBT and, as CFT is an adapted form of CBT, will be included in the current self-help intervention. The session content and homework exercises will build on previous sessions and homework, so there will be a clear sense of progression through the intervention. In addition, imagery and written homework exercises will be alternated, to provide variety and keep participants engaged in the intervention. A breakdown of the intervention is shown in Table 1. Examples relating to skin conditions will be given throughout the self-help materials.

Expert feedback regarding the content of the website has been sourced through personal contacts and social media. Feedback has already been gathered from three people with skin conditions. Changes to the website deemed necessary based on their

---

 Some participants may struggle with imagery exercises (Naismith, Mwale, & Feigenbaum, 2018) while others may prefer imagery to written exercises. Alternating these types of homework task ensures that participants are never asked to do their less-preferred type of task for two consecutive weeks.

feedback have been made (see Appendix K for anonymised email exchanges with expert patients). In addition, a clinician with expertise in CFT has agreed to provide feedback on the intervention, and any minor amendments (e.g. re-phrasing items) recommended to keep the intervention in line with CFT principles will be made. The Psychology DESC will be informed if any substantial amendments (e.g. changes to the format of the intervention) are recommended.

## Measures

**Demographics.** As part of the baseline measures, participants will be asked to provide demographic information about their age, gender, ethnicity, country of residence, employment status and education level.

**Clinical information.** Participants will be asked to state the name of their skin condition(s) and how long they have had the condition. Participants will also be asked to indicate whether they are currently taking any medication for a mental health condition, and if 'yes', what medication(s) they are taking and how long they have been taking it.

**Acceptability measures.** Overall acceptability: At the end of the intervention, participants will be asked to provide feedback via Qualtrics about which aspects of the intervention were helpful or unhelpful for them and if they can identify any areas for improvement. Open questions with spaces for text responses will be used to collect this feedback, as well as an adapted version of the 'Friends and Family Test' used in the NHS (see Appendix J). In line with recommendations that internet interventions monitor negative effects (Rozental et al., 2014), participants will also be asked whether the intervention exacerbated any existing symptoms or caused any novel symptoms to arise.

Acceptability of intervention components: Participants will be asked for their feedback on each weekly session of the intervention. Weekly feedback measures avoid retrospective bias and responses will be used to identify helpful/unhelpful aspects of the self-help intervention for further intervention development. Likert scales will be used to ask participants for feedback on the usability of the webpage and the impact of the self-help session. Relevant items from the Website Evaluation Questionnaire (Elling,

2012) and the Session Impacts Scale (Elliott & Wexler, 1994) will be adapted to form these Likert scales (see Appendix I). In addition, participants will have the opportunity to make other comments on the weekly sessions via open text responses. Self-reported adherence to the homework exercises will not be assessed, as the activities will differ from session to session, so it will not be possible to calculate overall adherence with the homework exercises.

**Outcome measures.** The depression subscale of the DASS (DASS-DEP; Lovibond & Lovibond, 1995) will be used to measure participants' levels of depression. This consists of 14 items. Participants are asked to rate how much statements applied to them over the past week on a four-point scale from 'did not apply to me at all' (0) to 'applied to me very much, or most of the time' (3), for example, 'I couldn't seem to experience any positive feeling at all'. Higher scores indicate higher levels of depression. Internal consistency of the DASS-DEP is excellent, with Cronbach's alpha of .95 (Crawford & Henry, 2003).

The Self-Compassion Scale (SCS; Neff, 2003) is a 26-item scale that will be used to measure participants' levels of self-compassion. Participants are asked to rate how often they behave in the manner described in the statements on a five-point scale from 'almost never' (1) to 'almost always' (5), for example, 'When I'm going through a very hard time, I give myself the caring and tenderness I need'. Half the items are negatively worded, and the total self-compassion score is obtained by reverse coding the negative items. Higher scores indicate higher levels of self-compassion. The SCS has been shown to have excellent internal consistency, with a Cronbach's alpha of .93 (Neff & Pommier, 2013). The SCS can also be used to give subscale scores for its six components: self-kindness, self-judgement, common humanity, isolation, mindfulness and over-identification. The subscale scores have acceptable internal consistencies, with Cronbach's alphas between .75 and .81 (Neff, 2003).

The Dermatology Life Quality Index (DLQI; Finlay & Khan, 1994) will be used to measure the impact of participants' skin conditions. Participants are asked to rate how much their skin condition has affected different areas of their life over the last week on a

four point scale from 'not at all/not relevant' (0) to 'very much' (3), for example, 'Over the last week, how much has your skin affected any social or leisure activities?' Higher scores indicate more impaired quality of life. A review of studies that used the DLQI found Cronbach's alpha ranged from 0.75 to 0.92 (Basra, Fenech, Gatt, Salek, & Finlay, 2008).

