While there are many published studies on CFT (see Beaumont & Hollings Martin, 2015; Leaviss & Uttley, 2015, for reviews), research on self-help based on CFT is in its infancy. Despite this, CFT-based self-help has been shown to improve depression in a variety of populations: students (McEwan & Gilbert, 2016), self-critical people (Krieger, Martig, van der Brink, & Berger, 2016; Krieger et al., 2018), people with low-moderate wellbeing (Sommers-Spijkerman, Trompetter, Schreurs, & Bohlmeijer, 2018) and perinatal and intending-to-become-pregnant women (Kelman, Evare, Barrera, Muñoz, & Gilbert, 2018). Furthermore, two of these studies found that treatment gains were maintained at six-month follow-up (McEwan & Gilbert, 2016; Krieger et al., 2018), and one found that online CMT was superior to online CBT for depression (Kelman et al., 2018).

Although psychological interventions are intended to improve people's lives, negative emotions and distress are common side effects, for example, affecting around 27% of CBT patients (Schermuly-Haupt, Linden, & Rush, 2018). As well as demonstrating benefits from their self-help interventions, three of the above studies investigated negative effects. McEwan and Gilbert (2016) concluded that compassion-focused imagery could safely be practised using online instructions without clinical supervision, as only two participants (4.4%) reported experiencing negative emotions (pity and sadness) while trying to feel compassion. Contrary to concerns that people who were highly self-critical might show adverse responses, the higher self-critics showed the largest improvements. Similarly, in Krieger et al.'s (2016) pilot study only four participants (10.3%) experienced negative emotions (sadness and shame) during the programme—but the three people who felt sadness said that this then helped them to become more self-compassionate. In the subsequent randomised trial, four participants (6.8%) in the compassion group experienced negative emotions during the intervention (loneliness, impatience, anxiety, sadness and emotional instability), most of

---

 Krieger et al. (2016) and Krieger et al. (2018) investigated an online version of the 'Mindfulness-Based Compassionate Living' programme, which, although not explicitly based on CFT, also uses Gilbert's (2010) theoretical framework of three affect regulation systems.

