## **Acceptability and feasibility criteria**

Acceptability of intervention overall: The percentage of eligible participants who access the webpages will be calculated using Qualtrics data and user logins to the website. The intervention will be considered acceptable if at least 66% of eligible participants log into the website during their sixth week of the study. This criterion was chosen as a recent meta-analysis of computerised CBT for depression and anxiety disorders reported a median retention rate of 66% (Andrews et al., 2018).

Feasibility of providing online self-help: All eligible participants should be able to access the website, so if less than 90% of eligible participants log into the website during their first week of the study, this may suggest that there were problems with accessing the self-help website. This criterion was chosen as more than one in ten people having

difficulty accessing the website is analogous to experiencing a ‘very common’ side effect of a medication (NHS, 2018). User logins for subsequent weeks of the intervention will also be recorded.

Feasibility of providing guidance: Researcher time spent providing email guidance will be recorded, and will be considered feasible if this takes 120 minutes or less per patient over the study period. This criterion is derived from guidance on individual guided self-help interventions for people with depression, which typically consist of up to 240 minutes overall (up to eight sessions at 30 minutes each; NICE, 2010; National IAPT Programme, n.d.): if providing email guidance takes over half the amount of time needed for individual guided self-help programmes, then it cannot reasonably be argued to be “limited facilitation” (NICE, 2010, p. 23). The percentage of participants who requested additional support via email will also be recorded. These figures will inform future trials and implementation of guided self-help for people with skin conditions within health services.

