## Procedure

Data will be collected using Qualtrics, an online survey provider. In the study advert, participants will be provided with a link to the Qualtrics survey page, where they will read the participant information sheet and complete an online consent form (see Appendices A and B). Screening questions relating to the exclusion criteria will be asked before participants complete the demographic questions, clinical information, and baseline measures (see Appendices C–H). Baseline DASS depression scores will be calculated automatically by Qualtrics. Any participants who disagree with the consent statement or who are ineligible for the study will be re-directed to an ‘end of study’ webpage. This will explain that they are not able to continue with the study and recommend that they contact their GP if they need further support. Signposting information about mental health resources and emotional support for skin conditions will also be provided to all participants.

Qualtrics will notify the lead researcher when an eligible participant has completed the baseline survey. Eligible participants will be registered as users on the study website by the researcher and then sent an email with their login details and a link to the study website, with instructions to access the first session of the intervention. Anyone that attempts to access the intervention webpages without logging in will be redirected to the login page—the only exceptions to this are the homepage and the contact page. Requiring participants to log in means that engagement with the intervention can be monitored without involving any third parties for website traffic statistics (for example, Google Analytics), and also means that each participant’s use of the website can be accurately tracked no matter what devices they use. At the end of the first session, participants will be asked to provide feedback on the first session, which will be collected using Qualtrics. Participants will receive an automated email three days after completing the baseline measures to remind them to practise the homework exercise (or go through the session if they haven’t already done so). One

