week after completing the baseline measures participants will receive an automated email inviting them to access the second session of the intervention. Automated emails will continue to be sent in this way, with homework reminders and links to subsequent sessions. The emails will also invite the participant to contact the researcher if they require further support with the self-help materials. The researcher will respond to any such emails individually. One week after the last session participants will be invited to provide feedback via Qualtrics about the guided self-help intervention overall, and to complete the outcome measures again.

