## Ethical issues

**Ethical approval.** The proposal, information sheet, consent form, measures and intervention exercises for the current study will be sent to the University of Sheffield Department of Psychology Research Ethics Sub-Committee for approval through the online ethics application system. In addition, the University of Sheffield's research governance procedure will be followed, including completion of the 'Risk Assessment Checklist for University Sponsored Human-Interventional Studies' and public registration of the study on 'ClinicalTrials.gov'.

**Informed consent.** All potential participants will read an information sheet (see Appendix A) and complete a consent form (see Appendix B) online prior to taking part in the study. They will have the opportunity to ask the researcher any questions about their participation in the study via email. The researcher's email address will be provided on the information sheet.

**Participant withdrawal.** Participants will be able to withdraw from the study at any point until their data are anonymised. Participants will be informed of this on the information sheet and may contact the researcher by email to request that their data is destroyed should they subsequently wish to withdraw from the study.

Eight of the guided self-help emails will be automatically sent from Qualtrics based on completion of the baseline measures. If any participants contact the researcher to withdraw from the study, that participant's Qualtrics data will be exported (for ITT analyses) and then the participant's contact details will be deleted from Qualtrics so that further automatic emails are not sent to that participant.

**Adverse effects.** As with all psychological interventions, there is a risk that taking part in this study may raise participants' awareness of pre-existing distressing thoughts and feelings, leading to some distress during or after taking part in the study. Participants will be made aware of this possibility prior to taking part in the study via the information sheet (see Appendix A). The information sheet will also provide participants with signposting information for mental health support (e.g. the Samaritans) and advise them to speak to their GP if necessary. In addition, if

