participants advise the researcher of any adverse effects via email, the researcher will be able to re-iterate options for further support as appropriate. The researcher previously worked in primary care mental health services for five years, providing guided self-help to people with depression and anxiety disorders, and is therefore experienced in dealing with emotional distress and signposting appropriately. If necessary, the researcher will discuss concerns with her primary supervisor, who is a clinical psychologist.

**Confidentiality.** Participants will be informed that their data will be kept confidential and that they will not be personally identifiable in any results of the study. Unique identification numbers will be used throughout the data sets. A data file will be created to contain participants' details and their identification numbers, for matching up quantitative data over time and to allow the destruction of data should participants wish to withdraw from the study. This data file will be password-protected and kept separately from the rest of the participants' data.

Spreadsheets containing participants' names and email addresses will also be created in order to administer the study—for sending emails on the correct dates and tracking participants' logins. No sensitive quantitative data will be kept in these spreadsheets, only dates. These spreadsheets will also be password-protected and kept separately from outcome measures and feedback data. Once data collection is complete, participants' names and email addresses will be replaced with their unique identification numbers.

Participants will be required to log into the study website solely to track user logins for the purpose of monitoring participants' engagement with the intervention from week to week. Participants will log into the website with a username (usually their first name) and password that has been allocated to them by the researcher.

Participants will not be asked to provide any data via the study website, nor will they be able to access any other participants' details. No-one except the researchers involved in the study will have access to participants' contact details.

**Data protection.** Personally identifiable digital data will be stored securely as described above, on the lead researcher's university filestore. The lead researcher will be

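### The only explicit negative-effects question described is in the end survey, and none is described for people who withdraw, so prompted harm data may be missing for leavers.

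*Combined protocol and SAP*

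**What the plan says.** The plan sets out to monitor negative effects, citing recommendations for internet interventions. The Measures section places the question under overall acceptability, at the end of the intervention: "participants will also be asked whether the intervention exacerbated any existing symptoms or caused any novel symptoms to arise". The Procedure section fixes the timing: "One week after the last session participants will be invited to provide feedback via Qualtrics about the guided self-help intervention overall".

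Forms are also collected earlier. The Procedure section states: "At the end of the first session, participants will be asked to provide feedback on the first session, which will be collected using Qualtrics". The Measures section extends this feedback to every weekly session, with rating scales on webpage usability and session impact (items in Appendix I) and space for comments. The body text mentions no item on worsened or new symptoms in these weekly forms.

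For someone who asks to withdraw, the Ethical issues section says that the data are exported and the "contact details will be deleted from Qualtrics so that further automatic emails are not sent to that participant". No exit question is described. The same section foresees unsolicited reports: if "participants advise the researcher of any adverse effects via email, the researcher will be able to re-iterate options for further support as appropriate". It does not say that such reports are logged or counted.

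The Data analysis strategy gives no summary or denominator for negative effects. Its content analysis covers text from the overall feedback only.

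**The concern.** As written, the plan prompts for harm only once, at the point where those who left are least likely to answer. This sits awkwardly with the plan's own reasoning. The Measures section justifies weekly feedback as a guard against recall problems, yet the harm question asks people to look back over the whole programme. The background section on psychological treatments also reads high attrition in an earlier psoriasis trial as a sign of poor acceptability, which implies that leavers can be informative.

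What is at stake is how complete the monitoring is. The background uses counts from earlier compassion self-help studies as evidence of few adverse effects, for example "only two participants (4.4%) reported experiencing negative emotions (pity and sadness) while trying to feel compassion". Readers may use this study's count in the same way. Without a stated denominator, a person who never answered could be read as unharmed. A question not asked during the study cannot be added afterwards.

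**Working it through.** **Inputs.**
- Minimum recruitment 23 for 12 completers, planning attrition 48% (75th percentile of studies in a meta-analysis), maximum sample 54: Sample size section.
- Median retention 66%, so 100% − 66% = 34% not retained: Acceptability and feasibility criteria.
- Assumption: everyone lost to attrition also leaves the end survey unanswered. The documents do not give an end-survey response rate or a number of formal withdrawals.

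**The plan's own figure.** 12 / (1 − 0.48) = 23.08, stated as 23. Going the other way, 23 × 0.52 = 11.96, or about 12. The figure is reproduced to within one participant, which has no bearing here.

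**Participants with no answer to the prompted question** = number recruited × attrition:

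| Recruited | Attrition | No answer | Answering |
|---|---|---|---|
| 23 | 34% | 7.8, about 8 | about 15 |
| 54 | 34% | 18.4, about 18 | about 36 |
| 23 | 48% | 11.0, about 11 | about 12 |
| 54 | 48% | 25.9, about 26 | about 28 |

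If all leavers answer, the first count is 0. The table therefore gives the number missing when all leavers are silent, at two attrition levels.

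**Does this bias the rate?** Let d be the share not answering, r the rate among those who answer and v the rate among those who do not. The rate in everyone is (1 − d)r + dv, while the survey shows r. For illustration only, take r = 6.8%, the figure the background gives for one compassion self-help trial:
- v = 6.8%: the true rate is also 6.8%. There is no bias, but 34% to 48% of cases go unrecorded by this question.
- v = 0: the true rate is 0.66 × 6.8% = 4.5% at d = 34%, and 0.52 × 6.8% = 3.5% at d = 48%. The survey overstates it.
- v = 27% (the background's figure for side effects of CBT, borrowed here as an assumption): 0.66 × 6.8% + 0.34 × 27% = 13.7%, and 0.52 × 6.8% + 0.48 × 27% = 16.5%. The survey understates it.

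The documents do not give v, so these lines show only that the direction is open. The 6.8% also counts negative emotions, whereas the plan asks about worsened or novel symptoms.

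**Why email reports need separate treatment.** Suppose 1 of 12 respondents reports an effect (8.3%) and one otherwise silent person emails to report another. Pooling gives 2 of 13 (15.4%). Silent people would then enter the denominator only when they report harm.

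**The case against.** The strongest reply is that the plan has other routes. Weekly ratings and comments are meant to identify unhelpful aspects, and the adapted impact items in Appendix I are not available here, so an equivalent item cannot be ruled out. Participants are warned about distress and can email the researcher. People who merely stop logging in are not described as being removed from the end-survey invitation, and the end question covers the whole intervention. Estimating a negative-effect rate is not among the Aims. All of this stands. It means that the firm gap is among formal withdrawers, whose number is not given, and that the table may overstate the loss. It does not supply a prompted question for withdrawers or a reporting rule.

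Three stronger readings are tempting but unsupported.
- A reader might infer that the recorded rate will be too low. That needs leavers to be harmed more often than responders, which the documents do not show.
- A reader might infer that withdrawers cannot be reached. Their details are deleted from Qualtrics only. Separate spreadsheets with "names and email addresses will also be created in order to administer the study", and withdrawal requests come by email, so the reply can carry a question.
- A reader might infer from the 90% first-week login criterion that a session 1 item would capture harm in nearly everyone. That figure is a threshold, not a forecast, and logging in is not completing a form. The form also comes at the end of session 1, before most of the programme: Table 1 introduces imagery in session 3 and letter writing in session 4. Rates from whole programmes or imagery exercises cannot be applied to it.

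**Conclusion.** The point holds as a cheap improvement. The only explicit negative-effects question described is in the end survey, and none is described at withdrawal. Prompted data may be missing for about 8 of 23 (18 of 54) participants at 34% attrition and about 11 of 23 (26 of 54) at 48%, on the assumption that every leaver is silent. The number could be smaller, down to none. The loss of answers does not depend on whether leavers fare worse, but any bias in the rate does, and its direction and size are unknown. No acceptability or feasibility criterion changes. Confidence is medium, chiefly because Appendix I could not be seen.

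**What to change.** 1. Unless Appendix I already has an equivalent, add one short negative-effects item to each existing weekly Qualtrics form, and keep the question in the end survey.
2. Include one optional question in the reply to a withdrawal request, covering the reason for leaving and any negative effect.
3. In the Data analysis strategy, state that the number with a negative effect will be reported among those who answered the prompted item. Give the number of respondents at each time point and the number enrolled who never answered. Do not count non-responders as unharmed. List unsolicited email reports separately, outside that proportion.

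**Cost.** Weekly forms become slightly longer, the researcher needs some time to read and answer reports, and the revised forms go into the ethics submission, which already covers the measures. No extra participants are needed. People who leave before completing any form and do not reply will still be missed.
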